6.5 Patient identification

After a patient has signed the PI/ICF for FGFR testing, the patient identification number will be provided to the investigators.

The patient number is a 9-digit number consisting of:

Digits 1 to 5 = Unique center number

Digits 6 to 9 = Current patient number within the center.

7. Treatments

7.1 Treatments to be administered

In Part A of the study, patients will receive a combination treatment of rogaratinib (a pan FGFR inhibitor) plus atezolizumab (a PD-L1 monoclonal antibody).

7.2 Identity of study treatment

In this protocol, the term "test drug" refers to rogaratinib only. The term "study drug" refers to any of protocol-stipulated drugs, i.e. rogaratinib or atezolizumab, and "study treatment" refers to the combination of rogaratinib and atezolizumab.

All study treatment will be labeled according to the requirements of local law and legislation. Label text will be approved according to the sponsor's agreed procedures, and a copy of the labels will be made available to the study site upon request.

For all study drugs, a system of numbering in accordance with all requirements of GMP will be used, ensuring that each dose of study drug can be traced back to the respective bulk batch of the ingredients. Lists linking all numbering levels will be maintained by the sponsor's clinical supplies QA group.

A complete record of batch numbers and expiry dates of all study treatment as well as the labels will be maintained in the sponsor's study file.

In case patients are transferred to a roll-over study or any other form of continued study drug supply with no cost to the patient, drug formulation and / or dosage might change compared to this study depending on the course of the clinical development.

23 MAY 2023 Version 6.0 Page: 53 of 181

In addition, the supply of commercially available non-Bayer drugs in a roll-over study or any other form of continued study drug supply with no cost to the patient will be at the discretion of the sponsor and can potentially change from central to local supply by the sponsor, to supply per prescription or any other available option.

7.2.1 Rogaratinib – test drug

Rogaratinib (BAY 1163877) is packaged in a wide-necked, child-proof HDPE plastic bottle (90ml) with 56 dark red coated tablets per bottle. Rogaratinib should be stored in the original container not above 25°C (77 °F).

Details of the test drug rogaratinib are given in Table 7–1.

Table 7–1: Identity of test drug (IMP): rogaratinib (BAY 1163877)

Generic name / brand name / INN	Rogaratinib
Formulation	Tablet
Substance code number(s)	BAY 1163877 (BAY 1213802, hydrochloride of BAY 1163877)
Material	BAY 1163877 hydrochloride coated tablet 200mg
Galenical form / formulation / vehicle and reconstitution	IR (immediate release) tablets
Composition	Active ingredients: BAY 1163877 as hydrochloride
	Other ingredients:
	Cellulose microcrystalline (filler)
	Lactose monohydrate (filler)
	Crospovidone (disintegrant)
	Copovidone (binder)
	Magnesium stearate (lubricant)
	Silica colloidal anhydrous (glidant)
	Lacquer red (coating material) ^a
	^a (contains hypromellose, macrogol, titanium dioxide, ferric oxide red)
Strength	200 mg BAY 1163877 per tablet
Type of packaging and content	HDPE bottles with screw cap closure sealable to PP (4345 / 0202)
Marketing Authorization Holder	Not applicable

HDPE = High-density polyethylene; IMP = Investigational medicinal product; INN = International Nonproprietary Name; IR = Immediate release; PP = Polypropylene.

7.2.2 Atezolizumab – combination drug

The study drug atezolizumab serves as the combination drug in this study Part A. Atezolizumab received accelerated FDA and full EMA approval for the treatment of metastatic urothelial carcinoma who have been previously treated with a platinum-based chemotherapy or who are considered ineligible for cisplatin chemotherapy (18, 31). Atezolizumab will be sourced centrally by the sponsor. For full details on atezolizumab and

23 MAY 2023 Version 6.0 Page: 54 of 181

instructions for dilution, please refer to the current Summary of Product Characteristics (SmPC) or the investigator's brochure. (Note: the SmPC should only be referred to for the preparation instructions for atezolizumab. The IB should be the reference for all other information about atezolizumab).

Please also refer to atezolizumab label for guidance when prescribing with other medications.

Atezolizumab vials should be stored under refrigeration at 2°C to 8°C (36°F to 46°F) in the original carton to protect from light. They should not be frozen or shaken.

7.3 Treatment assignment

In Part A, all eligible patients will be assigned to receive the same combination treatment, rogaratinib plus atezolizumab.

7.4 Dosage and administration

7.4.1 Doses, dosing schedule and route of administration

7.4.1.1 Rogaratinib – test drug

Rogaratinib will be administered orally in a stepwise dose selection schedule shown in Table 7–2 until disease progression, unacceptable toxicity or consent withdrawal.

Patients will receive their initial dose of 800mg rogaratinib in the morning of Cycle 1 Day 1, followed by serial PK blood sampling for 8 hours and a second dose of 800mg rogaratinib in the evening. Rogaratinib will be administered continuously twice daily on all 21 days in each cycle.

Special considerations/instructions for rogaratinib

Rogaratinib tablets should be taken with a glass of water (approximately 200 mL / 7 ounces). Tablets should be swallowed intact and not chewed. Rogaratinib tablets can be taken with or without food.

It is important to take the medications at the same times each day approximately 12 hours apart. For the second dose of rogaratinib on C1D1, a time window of \pm 3 hours is permitted. If a dose of rogaratinib is missed, the prescribed dose should be taken as soon as the patient remembers and up to 3 hours after the usual time. If this is not possible, the patient should miss the dose and continue with the next dose at the next prescribed interval.

Rogaratinib and atezolizumab will be dosed at the same time, starting first with the infusion and shortly after start (< 5 minutes) the intake of rogaratinib.

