	 To assess the efficacy of the combination of rogaratinib and atezolizumab in this patient population.
	 To characterize the pharmacokinetics (PK) of rogaratinib in combination with atezolizumab in this patient population
	Exploratory objectives of Part A:
	 To assess new potential predictive or prognostic biomarkers and their association with tumor-related biomarkers, disease response, drug-resistance and patient outcome.
	To evaluate further biomarkers to investigate the drug (i.e. mode-of-action-related effect and / or safety) and / or the pathomechanism of the disease.
	To evaluate the combination of rogaratinib and atezolizumab with regard to patient-reported outcomes (PRO).
Test drug	Rogaratinib / BAY 1163877
Name of active ingredient	Rogaratinib
Dose	The RP2D will be determined in Part A of the study. Starting dose level of rogaratinib is 800 mg twice daily (b.i.d.), in continuous 21-day cycles. If suggested by safety findings, lower doses may be explored.

23 MAY 2023 Version 6.0 Page: 5 of 181

Route of administration	Oral		
Duration of treatment	Oral Patients will continue dosing until any of the following occurs: • Radiological disease progression according to Response Evaluation Criteria in Solid Tumors version 1.1 (RECIST v1.1) • At the investigator's discretion, study treatment may continue beyond radiological progression as defined by RECIST v1.1 (e.g. in case of suspected pseudoprogression) if the clinical condition of the patient is stable or the patient is improving symptomatically, and the investigator expects continued clinical benefit for the patient. • Clinical progression • Unacceptable toxicity • Death • Consent withdrawal • Withdrawal from the study treatment at the discretion of the investigator or designated associate(s)		
Combination drug	Atezolizumab		
Name of active ingredient	Atezolizumab		
Dose	1200 mg every 21 days		
Route of administration	Intravenous (i.v.) infusion		
Duration of treatment	See test drug above		
Indication	FGFR-positive locally advanced or metastatic urothelial carcinoma		
Diagnosis and main criteria for inclusion /exclusion	Patients with FGFR-positive locally advanced or metastatic urothelial carcinoma who are cisplatin-ineligible and have had no prior systemic treatment for locally advanced or metastatic disease.		
	Main inclusion criteria:		
	 Male or female patients ≥ 18 years of age (at least age of legal maturity) 		

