Dose selection: The dose selection part of the study 19131 will assess the safety and tolerability of the combination. The maximum tolerated dose (MTD) and/or recommended Phase 2 dose (RP2D) for the combination will be determined using stepwise dose selection design based on a modified toxicity probability interval (mTPI) method (See Section 10.3.4.1). After dose selection, further patients (up to 50 in total for the whole Part A) will be enrolled to confirm the RP2D.

The study is composed of the following study periods:

- Pre-treatment period, including
 - o FGFR testing

23 MAY 2023 Version 6.0 Page: 8 of 181

The mRNA expression of FGFR1 or 3 will be investigated using archival or fresh tumor biopsy specimen taken before the screening procedures are conducted. Only patients with locally advanced or metastatic urothelial carcinoma whose tumors are FGFR positive (RNAscope score of 3+ or 4+) will be included in the study.

Screening

• Treatment period

Patients who meet all study inclusion and exclusion criteria will be eligible to start study treatment.

Patients will receive an oral, single dose of rogaratinib in the morning of Cycle 1 on Day 1, followed by single dose serial PK blood sampling for 8 hours and a second single dose of rogaratinib in the evening. Rogaratinib will be administered continuously twice daily on all 21 days in each cycle.

A fixed dose of 1200 mg atezolizumab will be administered through intravenous (i.v.) infusion on Day 1 of each 21-day cycle.

Patients will continue dosing of both study drugs until any of the following occurs:

- Radiological disease progression according to RECIST v1.1
 - At the investigator's discretion, study treatment may continue beyond radiological progression as defined by RECIST v1.1 (e.g. in case of suspected pseudoprogression) if the clinical condition of the patient is stable or the patient is improving symptomatically, and the investigator expects continued clinical benefit for the patient.
- Clinical progression
- Unacceptable toxicity
- Death
- Consent withdrawal
- Withdrawal from the study treatment at the discretion of the investigator or designed associate(s).

• Follow-up period

After primary completion, follow-up information will not be collected after the safety assessment visit.

Active follow-up

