dose level (800 mg b.i.d. being the highest possible dose), 'S'=stay at the current dose level, 'D'=de-escalate to next lower dose level and 'DU'= de-escalate to next lower dose level and exclude the current and higher dose levels from the further dose escalation due to unacceptably high toxicity (see Table 7–2 for rogaratinib dose levels). If the probability that a dose is above the MTD is greater than 95%, the dose will be declared as toxic and only lower doses will be given in subsequent cohorts. If the highest dose is reached, escalation ('E') leads to staying at that dose. At the lowest dose level de-escalation ('D') or de-escalation with unacceptable high toxicity ('DU') lead to stop of the study. Details are provided in Section 10.3.4.1

Intra-patient dose escalation is not permitted.

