7.4.3.2 Dose modifications of rogaratinib

Dose of rogaratinib may be interrupted / delayed or reduced in case of clinically significant toxicities that are related to study drug therapy. The intensity of toxicities will be graded using the CTCAE v 4.03.

If a patient experiences a DLT during Cycle 1 (Days 1-21), the next dose of rogaratinib can be delayed for up to 21 days. This is permitted also in case of Grade 3 toxicities that are not defined as withdrawal criteria and that are persisting ≤ 7 days.

All patients who are re-treated following a DLT should undergo dose reduction of rogaratinib (see Table 7–2).

If the toxicity resolves within 21 days after the planned treatment date to \leq Grade 1 re-starting rogaratinib at 1 dose level below the current dose can be considered (see Table 7–2). If such an improvement is not observed, the study treatment should be permanently discontinued.

Patients who experience a Grade 4 non-hematological toxicity, and any other toxicity defined as withdrawal criteria will be permanently withdrawn from the study treatment.

If a patient experiences clinically relevant toxicity after Cycle 1, the next dose of rogaratinib can be delayed for up to 21 days. This is permitted also in case of Grade 3 toxicities that are not defined as withdrawal criteria and that are persisting ≤ 7 days. If the toxicity resolves within 21 days after the planned treatment date to \leq Grade 1 or baseline, reduction of the next dosing of rogaratinib by 1 dose level below the current dose (see Table 7–2) can be considered.

Patients requiring dose reduction to less than 400 mg b.i.d. should be permanently withdrawn from the study treatment.

23 MAY 2023 Version 6.0 Page: 58 of 181

Table 7–2: Dose levels of rogaratinib (BAY 1163877)

Level	Dose
Starting level	800 mg b.i.d.
-1	600 mg b.i.d.
-2	400 mg b.i.d.

b.i.d = Twice daily, bis in die.

Dose modifications will be based on the highest intensity grade of AE since last contact.

If a patient experiences multiple toxicities, dose modification should be according to the toxicity with the highest grade.

- In case of multiple toxicities of the same grade, investigator should modify the dose using the most conservative approach, i.e. the lowest recommended dose.
- Patients in whom doses are interrupted due to toxicities should be followed up within 7 to 10 days to re-assess toxicities, if not specified otherwise.

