- I: For monitoring purposes of atezolizumab, blood (plasma) samples will be collected at the following time points: at Cycle 1 Day 1: pre-dose, 1 (EOI), 4 and 8

Integrated Clinical Study Protocol No. BAY 1163877 / 19131 Part A

23 MAY 2023 Version 6.0 Page: 92 of 181

Table 9–2: Schedule of evaluations: Treatment and follow-up periods

hours post-dose; and at Cycle 1 Day 15: approximately 336 hours post-dose.

- m: From signing of PI/ICF for study treatment eligibility up to 30 days after the last administration of study treatment, all concomitant medications (including start/stop dates, dose, frequency, route of administration and indication) must be recorded in the patient's source documentation, as well as on the appropriate pages of the eCRF.
- n: To have complete control over the distribution and use of the study drug, the drug accountability must be performed before new medication is handed out to the patient. Return of rogaratinib and diary at EOT visit.
- o: Patients will receive their initial single-dose of 800 mg rogaratinib in the morning of Cycle 1 Day 1, followed by serial PK blood sampling for 8 hours and a second dose of 800 mg rogaratinib in the evening. Rogaratinib will be administered continuously twice daily on all 21 days in each cycle. Oral administration of the morning dose of rogaratinib on Cycle 1, Days 1, 2, 8 and 15, and on Day 1 of subsequent cycles will be done with a member of the site.
- p: The radiological evaluation must include computed tomography (CT) or magnetic resonance imaging (MRI) of the chest, abdomen and pelvis with contrast media. Tumor assessments (CT or MRI) are to be done every 9 weeks (± 7 days) starting from Cycle 1 Day 1 until confirmed radiological disease progression or end of the study. After primary completion, scans will be performed every 14 weeks (±14 days). A minimum of at least 9 weeks from start of treatment is mandatory for the 1st "on treatment" tumor assessment. Formal efficacy assessment will be done according to RECIST v1.1. iRECIST will be assessed as exploratory endpoint.
- q: Radiological tumor evaluation (within 14 days after permanent discontinuation of study treatment). This is not necessary if the previous tumor evaluation was performed within 4 weeks (up to week 18) or within 7 weeks (beyond week 18).

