The UPM for a given interval is defined as the probability of the interval divided by the length of the interval. Then an appropriate dose-finding action will be chosen based on the interval with the largest UPM. Specifically, if the UPM for the under-dosing interval is the largest, the dose is considered lower than the MTD and the recommendation is to escalate to the next higher dose or to stay on the dose level if current dose is the highest possible dose (800 mg b.i.d. being the highest possible dose) (letter E in Table 10–1); if the target dosing interval has the largest UPM, the mTPI design will recommend remaining at the current dose (letter S in Table 10–1); if the over-dosing interval has the largest UPM, the design will recommend de-escalating to the previous lower dose (letter **D** in Table 10–1). If the safety stopping rule is met, the toxicity of the current dose will be considered as unacceptable high and never be used again in the remainder of the trial (letters **DU** in Table 10–1). The safety rule is triggered if the posterior probability that the current dose is above the MTD is greater than 95%. All of these rules are summarized and precalculated in Table 10-1 below. No decision is made before data of at least 4 patients are available on the first dose level and are evaluable for DLTs. The sponsor in consultation with the investigators will decide how many additional patients need to be evaluable for DLTs on the same dose level before the next decision. See Table 7–2 for rogaratinib dose levels.

The decision on the number of additional patients and on the next dose level will be based on the recommendations from the mTPI, clinical assessment, all available PK and safety data.

The dose selection part will be finished after 20 patients are evaluable for DLT assessment and are available for the MTD determination. The RP2D will be defined once sufficient data is available. The final decision about the RP2D will be made by the sponsor in consultation with the investigators.

23 MAY 2023 Page: 139 of 181 Version 6.0

Table 10-1: Possible dose finding actions

	Number of patients treated at current dose																
Number of patients with observed DLTs	4	5	6	7	8	9	10	11	12	13	14	15	16	17	18	19	20
0	Е	Е	Е	Е	Е	Е	Е	Е	Е	Е	Е	Е	Е	Е	Е	Е	Е
1	S	S	Ε	Е	Ε	Ε	Ε	Ε	Е	Ε	Ε	Е	Ε	Ε	Ε	Е	Е
2	S	S	S	S	S	S	S	Ε	Е	Ε	Ε	Е	Ε	Ε	Е	Ε	Е
3	DU	D	S	S	S	S	S	S	S	S	S	S	Ε	Ε	Е	Е	Е
4	DU	DU	DU	D	D	S	S	S	S	S	S	S	S	S	S	S	S
5		DU	DU	DU	DU	DU	D	S	S	S	S	S	S	S	S	S	S

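### Protocol 7.4.1.1 and Table 9-2 footnote o fix both Cycle 1 Day 1 rogaratinib doses at 800 mg, which cannot hold for a cohort opened at 600 or 400 mg b.i.d. (minor)

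*Protocol*

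**What the plan says.** **The fixed amount.** Protocol Section 7.4.1.1: "Patients will receive their initial dose of 800mg rogaratinib in the morning of Cycle 1 Day 1"; the evening dose is also given as 800 mg. Table 9-2 footnote o: "Patients will receive their initial single-dose of 800 mg rogaratinib in the morning of Cycle 1 Day 1", again with an 800 mg evening dose. Neither text mentions a cohort or dose level.

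**The rules that allow lower cohorts.** Table 7-2 lists 800 mg b.i.d. as the starting level, with 600 and 400 mg b.i.d. below it. Under the toxicity rule in Section 5.1, "the dose will be declared as toxic and only lower doses will be given in subsequent cohorts". On what follows a triggered safety rule, Section 10.3.4.1 says: "the toxicity of the current dose will be considered as unacceptable high and never be used again in the remainder of the trial". Section 10.4 allows other rogaratinib starting doses, depending on tolerability.

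**Text that points to the intended meaning.** Section 7.4.1.1 opens by citing Table 7-2: "Rogaratinib will be administered orally in a stepwise dose selection schedule shown in Table". The Synopsis says "If suggested by safety findings, lower doses may be explored". It also gives the Day 1 instruction without a milligram figure: "Patients will receive an oral, single dose of rogaratinib in the morning of Cycle 1 on Day 1". The log for Amendment no. 1 explains that the 800 mg figure came in with Version 2.0 so that a single dose would not be taken to mean one tablet.

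**The concern.** A dosing instruction that is right only for the starting cohort is written as if it applied to every patient. In a cohort opened at 600 or 400 mg b.i.d., following it exactly gives two doses above the assigned level. If that cohort was opened after a DU decision, it gives a dose that the protocol forbids.

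The analysis consequence is specific. Cycle 1 Day 1 is the only serial rogaratinib profile, and it supplies Cmax and AUC(0-8) (Protocol 9.5.1, 9.5.2). Section 10.3.5 tabulates Cycle 1 concentrations by dose level and only lists those from Cycles 2 to 5. SAP 4.1 groups summaries by assigned dose. An 800 mg profile could therefore be reported as 600 or 400 mg, and any DLT in that cycle would count toward the lower level.

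**Working it through.** **1. Is a cohort below 800 mg reachable under the plan's rule?**

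Inputs, from Protocol 10.3.4.1: Beta(1,1) prior; intervals [0, 0.25], [0.25, 0.35] and [0.35, 1]; target 0.30; DU when the posterior probability of being above the MTD exceeds 0.95, taken here as P(p > 0.30). With x DLTs in n patients the posterior is Beta(1 + x, 1 + n − x). The unit probability mass (UPM) is interval probability divided by interval length.

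- 3 of 4: Beta(4, 2). UPM under/target/over = 0.062 / 0.384 / 1.455; P(p > 0.30) = 0.969. Action DU, as in Table 10-1.
- 3 of 5: Beta(4, 3). P(p > 0.30) = 0.930. Action D, as tabulated.
- 4 of 6: Beta(5, 3). UPM 0.052 / 0.427 / 1.453; P(p > 0.30) = 0.971. Action DU, as tabulated.

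So 800 mg can be excluded at the first permitted decision (4 patients). The chance of at least 3 DLTs in 4 is 4p³(1 − p) + p⁴:

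- p = 0.20: 0.0256 + 0.0016 = 2.7%
- p = 0.30: 0.0756 + 0.0081 = 8.4%
- p = 0.40: 0.1536 + 0.0256 = 17.9%

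**2. How likely is a lower-dose recommendation by 20 patients?**

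The documents give neither an expected DLT rate nor a fixed look schedule, so both are assumptions. The calculation is an exact recursion at 800 mg that stops at the first D or DU. The recomputed actions agree with the legible cells of Table 10-1.

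First call is DU:

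| Looks (patients) | p = 10% | 20% | 25% | 30% | 40% |
|---|---|---|---|---|---|
| 4/8/12/16/20 | 0.4% | 3.4% | 6.9% | 12.4% | 30.0% |
| 6/10/14/17/20 | 0.1% | 2.0% | 4.7% | 9.4% | 25.7% |
| every patient, 4 to 20 | 0.4% | 2.8% | 5.4% | 9.2% | 20.4% |

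First call is D or DU:

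| Looks (patients) | p = 10% | 20% | 25% | 30% | 40% |
|---|---|---|---|---|---|
| 4/8/12/16/20 | 0.8% | 7.2% | 14.4% | 24.7% | 52.1% |
| 6/10/14/17/20 | 0.3% | 4.4% | 10.5% | 20.4% | 49.1% |
| every patient, 4 to 20 | 1.1% | 9.2% | 17.7% | 29.3% | 57.9% |

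These are chances that the rule recommends a lower level, not chances of misdosing. Only DU bars 800 mg; a plain D does not.

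**3. Size of the dose discrepancy if the text is read literally.**

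Cycle 1 has 21 × 2 = 42 doses, of which 2 are on Day 1.

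- 600 mg cohort: 800/600 = 1.33, so +33% per Day 1 dose. Cycle total 40 × 600 + 2 × 800 = 25,600 mg against 42 × 600 = 25,200 mg; 400/25,200 = +1.6%.
- 400 mg cohort: 800/400 = 2.00, so +100% per Day 1 dose. Cycle total 40 × 400 + 2 × 800 = 17,600 mg against 42 × 400 = 16,800 mg; 800/16,800 = +4.8%.

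**4. Would the planned checks find it?**

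The administered dose is recorded in the eCRF (Protocol 7.7). Actual dose and percent of planned dose are summarized over the study (SAP 6.4). A validity review assigns analysis sets (SAP 4.6, 5.1), and important deviations can remove a patient from the PK set (Protocol 10.2). Any of these could expose a mismatch, but none names a comparison of the Day 1 dose with the assigned dose. An excess of 1.6% or 4.8% within one cycle is easy to miss in a whole-study percentage. The 80% rule for the MTD set is a lower bound, so an excess passes it.

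**The case against.** Read as a whole, the protocol shows what is meant. Section 7.4.1.1 opens with the stepwise schedule, and Table 7-2 labels 800 mg b.i.d. as the starting level. The Cycle 1 Day 1 visit description gives no amount and sends sites to Section 7.4. Site staff supervise the Day 1 morning dose and document that treatment is given as planned (7.7), which is the dose behind the PK profile. The mTPI output is guidance combined with clinical, PK and safety data, so a D recommendation need not open a lower cohort. Even if misdosing occurred, the concentrations would be valid 800 mg data with the administered dose on record. No Day 1 doses remain to be given: the Amendment no. 3 log says the remaining patients had been treated for at least two years.

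Most of this stands, and it makes misdosing unlikely. It does not make the wording right. Footnote o has no pointer to Table 7-2, and the visit description leads to a section whose first stated amount is 800 mg. Supervision checks the dose against the plan, and the plan says 800 mg; it also covers only the morning dose. Section 13.3 asks sites for strict adherence to the protocol's specifications. Valid 800 mg concentrations are still mislabelled if summarized under another assigned dose.

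**Conclusion.** The concern holds as a minor error of wording. Two operative dosing statements prescribe 800 mg for all patients and conflict with the cohort rules for any cohort opened below 800 mg b.i.d.; after a DU decision they prescribe a barred dose. Table 7-2 taken alone does not conflict, because a patient who starts at 800 mg and is later reduced fits both texts.

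If followed literally, the excess is 33% or 100% on each of two doses and 1.6% or 4.8% over Cycle 1, and the serial PK profile would be attributed to the wrong level. This depends on two things the documents do not show: that a lower cohort was opened, and that the sentence was applied to it. The probabilities above rest on assumed DLT rates and look schedules and show only that a lower cohort was a real contingency. No sample size, power or error rate changes.

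**What to change.** In Section 7.4.1.1 and Table 9-2 footnote o, for both the morning and the evening dose, replace the fixed 800 mg with: the dose level assigned to the patient's cohort (800 mg b.i.d. at the starting level; see Table 7-2).

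Because enrolment is over, the edit only corrects the record. The useful action now is a data check: for every patient who started below 800 mg b.i.d., compare the recorded with the assigned Day 1 doses during the validity review, before PK and DLTs are reported by dose level. If there were no such patients, say so in the study report.

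The cost is two phrase edits and one comparison of existing eCRF data, with nothing to check if every patient started at 800 mg b.i.d.
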